Coagulopathy following cardiac surgery may significantly impact postoperative outcomes by increasing blood loss, blood product transfusion, and risk of chest reexploration. Cardiac surgical patients are at increased risk for coagulation abnormalities and platelet dysfunction as a result of hemodilution and destruction by cardiopulmonary bypass. Early generation HES solutions have been associated with coagulation abnormalities.^{6,7} A recent meta-analysis of 18 randomized, controlled trials found increased risk of bleeding, blood product transfusion, and reoperation in patients who received HES solutions during cardiac surgery.⁸ Following this report, the FDA has added safety information, specifically, the risk of excess bleeding in cardiac surgical

patients, to the Warnings and Precautions section of the package insert of all HES products, irrespective of molecular weight or degree of molar substitution.^a It is important to note, however, that this report was limited by the fact that head-to-head trials comparing risk of bleeding of newer generation HES solutions, such as HES 130/0.4 with human albumin 5% have not been performed. In fact, this analysis⁸ extrapolated results from older generation HES solutions (HES 200/0.5) to the newer HES products, because a direct comparison was not available. Thus an investigation comparing coagulation abnormalities and platelet dysfunction between albumin and the newer HES products, namely HES 130/0.4 (Voluven) is necessary to examine the safety profile in adult cardiac surgical patients.

Cardiac surgical patients are also at risk for a vigorous inflammatory response, which, if severe, may significantly worsen postoperative clinical outcomes.⁹ This inflammatory response may also contribute to multiorgan system dysfunction that can manifest as pulmonary dysfunction, coagulopathy, renal insufficiency, myocardial dysfunction, and neurocognitive defects.^{10,11} Limited information suggests that HES solutions may provide beneficial antiinflammatory effects.¹² Efforts to protect kidney and pulmonary function and coagulation/platelet abnormalities while inhibiting this harmful inflammatory response may improve outcomes following cardiac surgery.

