- 5) Postoperative requirement for thoracentesis for treatment of pleural effusion

- 6) Occurrence of new-onset atrial fibrillation requiring medical therapy or cardioversion
- 7) Duration of surgery and anesthesia
- 8) Duration of mechanical ventilation (hrs)
- 9) Duration of stay in intensive care unit (days)
- 10) Duration of hospital stay (days)
- 11) Postoperative in-hospital mortality
- 12) In-hospital morbidities, including
 - a. Cardiac morbidity (postoperative myocardial infarction or low cardiac index with a requirement for mechanical circulatory support),
 - b. Neurologic morbidity (new postoperative focal or global neurologic deficit confirmed by clinical findings and/or computed tomographic scan),
 - c. Renal morbidity (new postoperative requirement for RRT), including reason for the requirement of RRT, and duration of RRT
 - d. Infection morbidity (culture-proven pneumonia, mediastinitis, wound infection or septicemia)
 - e. Overall morbidity (incidence of one or more of the above morbidities, including death, since early death precludes observation of morbidity)
- 13) Fitness for hospital discharge (using modified criteria published by Walji et al.²⁷)
- 14) Hospital readmission for fluid overload (including pleural effusion) within 30 ± 5 days following surgery
- 15) Hospital readmission for atrial fibrillation within 30 ± 5 days following surgery
- 16) Hospital readmission for any cause within 30 ± 5 days following surgery
- 17) All-cause mortality at 30 ± 5 , 90 ± 15 days and one year (± 1 month) following surgery from follow-up phone calls, the patient's primary care physician, or the Social Security Death Index.
- 18) Kidney function measured by serum creatinine and requirement for RRT and duration of RRT at $90 (\pm 15)$ days following surgery collected from medical records at the Cleveland Clinic or outside hospitals if available. Kidney function may be classified into RIFLE categories if adequate long-term data is available (RIFLE-L and RIFLE-E require follow-up data for 4 weeks to 3 months). The reason for RRT will be documented.
- 19) Renal function measured by serum creatinine and need for RRT between 6 months (± 1 month) and 1 year (± 1 month) following surgery collected from medical records at the Cleveland Clinic or outside hospitals/physician records if available. Kidney function may be classified into RIFLE categories if adequate long-term data is available. The reason for RRT will be documented.

Experimental protocol

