Patients will be randomized into either the HES 130/0.4 (HES) or standard care group (human albumin 5%) prior to induction of anesthesia (see Randomization above). The study drug (HES 130/0.4 (Voluven) or human albumin 5%) will be delivered to the operating room in similar

packaging and covered with a shroud to conceal the appearance of the solution (see Blinding and Unblinding above).

Intraoperative Fluid Management

On arrival to the operating room, a large-bore intravenous catheter will be inserted. Routine administration of crystalloid fluids will occur throughout the intraoperative period as a continuous infusion to provide carrier solutions for intravenous drugs, inotropic and vasopressor agents, and continuous flow to maintain patency of intravascular catheters. This routine crystalloid administration will consist of approximately one liter of fluid prior to initiation of cardiopulmonary bypass and one to two liters of crystalloid following cardiopulmonary bypass.

Following separation from cardiopulmonary bypass, the patient will be continuously monitored for acute hypovolemia requiring plasma volume replacement. Plasma volume replacement using 250 mL increments of the blinded study drug (HES 130/0.4 or 5% human albumin in similar containers and covered by a shroud) will be administered when indicated by any of the following clinical conditions (Figure 1): 1) the cardiac output/cardiac index experiences a 20% decrease from baseline; 2) the heart rate increases to 20% above baseline; 3) mean or systolic blood pressure decreases 20% from baseline; 4) a 20% increase in vasopressor requirement occurs; 5) a 20% decrease in cardiac filling pressures (central venous pressure, pulmonary artery diastolic pressures). When these conditions are met, the patient will receive 250 – 500 mL of study solution (HES 130/0.4 or 5% human albumin) as a fluid bolus. These parameters will be assessed on a continuous basis during the intraoperative period and the patient will receive the study solution each time these conditions are met. We anticipate that an average patient will receive approximately 750 – 1000 mL study solution during a routine cardiac surgical procedure.

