The randomized HES and standard therapy groups will be descriptively compared for balance on potentially confounding baseline variables (including duration of cardiopulmonary bypass, use of anti-fibrinolytic therapy, preoperative anticoagulant medications, including clopidogrel). Any baseline variable for which the standardized difference (i.e., observed difference in means or proportions divided by the pooled standard deviation of the outcome) is greater than 0.25 will be considered imbalanced and adjusted for as a covariate in each of the below analyses. We will not use P-values to determine baseline imbalance since the P-value is quite dependent on the sample size, whereas the standardized difference is more independent of sample size and thus a better assessment of balance. [A standardized difference of 0.25 is conservative (should be 0.39) based on the expected 2.5th and 97.5th percentiles of the sampling distribution, i.e., $1.96 \times \sqrt{2/n}$ per group = 50 = 0.39.]³⁰ For all analyses of continuous variables, transformations of the data will be made as appropriate to achieve normality and/or meet other model assumptions. If transformations are not successful, non-parametric analyses analogous to those described below will be employed. For example, we might employ a Wilcoxon rank-sum test to compare the groups on IL-6 at a particular time point if the data are not close to a normal or log-normal distribution.

All primary analyses will be modified intent-to-treat (M-ITT), such that the groups being compared will be all patients who are randomized and who undergo surgery. Analyses of the safety outcomes in Aims 1 and 2 will be noninferiority assessments, and so 1-tailed. All tertiary analyses will be 2-tailed tests for superiority. Conclusions about the effect of HES will be confirmatory for the primary outcome (urinary NGAL) and more exploratory for other outcomes. We will also conduct a “per protocol” analysis for the primary outcome and describe whether these results differ from the modified intent-to-treat results. In the per-protocol analysis we will analyze patients according to the treatment received as oppose to the randomized treatment, and only those patients who complete the entire trial according to the protocol will be included. In case of a discrepancy, the M-ITT results will be primary.

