Continuous outcomes measured over time (Primary and secondary aims). For the primary outcome (urinary NGAL) and each of the secondary continuous outcomes which are measured over time (e.g., at baseline, within one hour of arrival to ICU following surgery, and 24 hours following completion of surgery), we will assess the treatment effect of HES 130/0.4 versus standard care using linear mixed effects models (with patient as random effect), adjusting for the baseline value of the outcome and any baseline variables for which balance among the randomized groups was not achieved through randomization. We will adjust for the baseline value of the outcome for efficiency, i.e., to obtain a smaller standard error for the estimate of treatment effect to the extent that the baseline value is correlated with the later time points, regardless of baseline balance. An unstructured within-subject correlation structure will be employed, estimating a distinct correlation parameter for each pair of post-baseline measurement times.

If the treatment group-by-time interaction is significant ($P < 0.15$), the treatment effect for a particular outcome will be assessed at each of the post-baseline time points measured, using a Bonferroni (or other appropriate) correction for multiple comparisons procedure if comparing groups at specific time points. Similarly, correction to the significance criterion will be made in all analyses below when comparing multiple times, as appropriate.

Ordinal outcome. Groups will be compared on the ordinal outcome of the RIFLE criteria (Secondary Aim 1) using proportional odds logistic regression, adjusting for baseline imbalance

as needed. We will assess noninferiority using the approach described above for the primary outcome, where $\hat{\beta}_1$ is the estimated treatment effect in the form of a log-odds ratio.

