Time to event outcomes. Randomized groups will be compared on time to event outcomes including duration of mechanical ventilation, duration of stay in the intensive care unit, and duration of hospital stay using Cox proportional hazards regression models adjusting for any baseline imbalances covariables. For these models the outcome will be time to experiencing the event while alive, i.e., time to removing the ventilator, discharge from the ICU and discharge from the hospital. Patients who die before the event occurs will be listed as failures (i.e., no event) and censored at a time just beyond the last observed event for any patient. Ignoring the deaths or censoring at the time of death may introduce bias.

Binary outcomes. Groups will be compared on binary outcomes, including in-hospital cardiac, renal, infection, or neurologic morbidity, and overall major morbidity (including death), using either logistic regression (to adjust for baseline imbalance as needed) or Pearson chi-square or Fisher's exact test, as appropriate. However, the study is not powered for assessing binary outcomes, and these analyses particularly will be interpreted with caution (whether significant or not).

For all analyses, confidence intervals for the estimated treatment effect will be provided, and these, along with the point estimates of treatment effect, will be emphasized in our reporting. SAS statistical software (Carey, NC) and R software version 2.8.1 for Windows (The R Foundation for Statistical Computing, Vienna, Austria) will be used for all statistical analyses.

Missing data. If primary or secondary outcome data are missing we will use multiple imputation of outcome values based on all available data before the time point of interest. As a secondary analysis we will conservatively assign the worst observed value for the given time point across all patients to an HES patient and best observed value to a control patient. If there is a non-trivial amount of missing outcome data we will also conduct sensitivity analyses on various forms of imputation (from none at all to full multiple imputation). However, we will work hard to avoid missing outcome data. If baseline data not included in the analyses are missing we will simply describe the missingness.

Sensitivity analyses. We will conduct a sensitivity analysis for the primary outcome that adjusts for time on CPB, length of surgery and intraoperative hypothermia.

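### The sensitivity analysis of urinary NGAL adjusts for length of surgery, which is settled partly after study fluid starts and could absorb harm acting through bleeding

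*Combined protocol and SAP*

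**What the plan says.** Under Statistical Methods, the Sensitivity analyses paragraph sets out one covariate-adjusted analysis of the primary outcome, which "adjusts for time on CPB, length of surgery and intraoperative hypothermia". It gives no reason for choosing these covariates, no measurement window for hypothermia, and no caution about interpretation.

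Other sections fix the timing and status of these variables:

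- Experimental protocol: patients are randomized "prior to induction of anesthesia".
- Intraoperative Fluid Management: "Following separation from cardiopulmonary bypass, the patient will be continuously monitored for acute hypovolemia requiring plasma volume replacement", and "the patient will receive the study solution each time these conditions are met".
- First paragraph of Statistical Methods: bypass time is listed among "potentially confounding baseline variables (including duration of cardiopulmonary bypass". Length of surgery is not named there.
- Descriptive variables under Outcomes and Aims: "Duration of surgery and anesthesia" is an item to be reported and compared by group.
- Continuous outcomes measured over time: the primary model works by "adjusting for the baseline value of the outcome and any baseline variables for which balance among the randomized groups was not achieved through randomization".

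The introduction and the Background section on platelets and coagulation both cite a meta-analysis that found "increased risk of bleeding, blood product transfusion, and reoperation in patients who received HES solutions during cardiac surgery".

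**The concern.** The trial asks whether giving HES instead of albumin worsens NGAL by any route. A covariate that treatment can change is not a confounder of that comparison. Holding it constant asks a narrower question: the effect of HES among patients whose operations lasted equally long. Any harm that runs from HES to bleeding, to a longer operation, to higher NGAL is then taken out of the estimate.

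In a noninferiority trial the likely direction matters. Removing a harmful pathway moves the estimate toward noninferiority, so an analysis meant to challenge the primary result could support it for the wrong reason.

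**Working it through.** The plan attaches no figure to this analysis, so there is none to reproduce. The check sets out the timing and then an illustration on stated assumptions.

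**1. Order of events**

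- Randomization comes before induction.
- Bypass runs to separation. Bypass time is therefore complete before study fluid starts, unless the patient returns to bypass.
- Study fluid is given after separation, repeatedly as triggers occur.
- Protamine, decannulation and chest closure also follow separation (Anesthetic and surgical management). The section on transfusion describes treatment of bleeding after bypass in the same interval.
- Length of surgery is known only at the end of that interval, so part of it comes after exposure.
- Hypothermia has no stated window, so it cannot be placed before or after exposure.

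**2. What adjustment removes**

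Let *a* be the hours by which HES prolongs surgery and *b* the NGAL ratio per extra hour. In a linear model on the log scale with no shared causes of length and NGAL:

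adjusted log ratio = total log ratio − *a* × ln(*b*)

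If *a* = 0 or *b* = 1, nothing is removed.

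**3. Inputs from the plan**

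- Margin: ln(1.15) = 0.1398.
- Log-scale SD from the assumed CV of 25%: √ln(1 + 0.25²) = 0.2462.
- Maximum of 130 patients, so 65 per arm: SE = 0.2462 × √(2/65) = 0.0432.
- One-sided 0.025 test: the observed log ratio must be at most 0.1398 − 1.96 × 0.0432 = 0.0551, a ratio of about 1.057.
- Chance of declaring noninferiority: Φ[(0.1398 − adjusted log ratio)/0.0432 − 1.96].

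This is a fixed-sample normal approximation that ignores the interim looks.

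**4. Illustration at a true ratio of 1.15**

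The values of *a* and *b* are assumptions; the documents give neither.

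| *a* (h) | *b* per h | Adjusted ratio | Share of log effect removed | Chance of declaring noninferiority |
|---|---|---|---|---|
| 0 | any | 1.150 | 0% | 0.025 |
| 0.25 | 1.05 | 1.136 | 9% | 0.047 |
| 0.5 | 1.10 | 1.096 | 34% | 0.196 |
| 1.0 | 1.10 | 1.045 | 68% | 0.597 |

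For the third row: 0.1398 − 0.5 × 0.0953 = 0.0921, and exp(0.0921) = 1.096.

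A simulation of 4,000 trials for that row gave 1.151 unadjusted and 1.097 adjusted, with noninferiority declared in 2.6% and 20.0% of trials.

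**5. Shared causes**

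A simulated unmeasured factor that both lengthened surgery and raised NGAL took the adjusted ratio in the third row to 1.070. With that factor present, *a* = 0.5 and no effect of length on NGAL, the ratio was 1.123. With *a* = 0 it stayed at 1.150. A factor acting in opposite directions on length and NGAL would shift the estimate the other way, so the direction is likely but not certain.

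**The case against.** The documents nowhere show that HES 130/0.4 prolongs surgery. The Background describes its coagulation evidence as conflicting and says the cited meta-analysis extrapolated from an older starch. Reoperation in that meta-analysis is also not the length of the index operation. This stands: the pathway is plausible but conditional.

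A reader might infer that the adjustment would turn a harmful result into a finding of noninferiority. The documents do not support that. Suppose the true ratio were 1.20 and 20% to 30% of the log effect ran through longer surgery (assumed). The adjusted ratio would be exp(0.8 × ln 1.20) = 1.157 or exp(0.7 × ln 1.20) = 1.136. The first is still outside the margin. If observed, neither would pass the test in the working, which needs about 1.057 or lower. With those as true adjusted ratios, the chance of passing is about 1.8% and 4.7%. The larger probabilities in the table depend wholly on assumed inputs.

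There is also a defensible motive for the adjustment. Postoperative NGAL sampling is timed from ICU arrival or departure from the operating room, so a longer operation shifts sampling relative to bypass. The plan does not give this reason, and the adjustment would still remove any harm acting through length.

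Finally, duration of surgery is reported by group, so a difference between arms would be visible. That helps interpretation but does not restore the total effect in the adjusted estimate.

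**Conclusion.** The point holds, as a minor one. Length of surgery is settled partly after study fluid begins, and adjusting for it can hide harm that acts through bleeding and a longer operation. Whether it does so depends on two links that the documents do not quantify: that HES prolongs surgery, and that longer surgery raises NGAL. The size therefore cannot be derived, and without the first link the loss is nil.

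Three stronger readings should be avoided:

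- That the confirmatory conclusion is compromised. The primary modified intent-to-treat model does not name length of surgery, and the sensitivity analysis carries no decision rule.
- That hypothermia has the same defect. With no stated window its timing cannot be judged, and the documents describe no route from HES to hypothermia.
- That bypass time is beyond question. It is acceptable up to first separation, but a return to bypass would extend it past the start of study fluid.

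**What to change.** Amend the Sensitivity analyses paragraph so that the analysis uses only covariates settled before the first study-fluid dose:

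- bypass time up to first separation;
- where recorded, time from incision to end of bypass (first separation), in place of length of surgery;
- intraoperative hypothermia, defined as measured up to first separation from bypass.

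This keeps an adjustment for operative complexity. Go on reporting duration of surgery by group, as already planned. If a model adjusted for length of surgery is still shown, label it as not estimating the total treatment effect and do not cite it in support of noninferiority.

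The cost is a short change to the SAP wording, with no effect on design, sample size or patient care. The pre-separation interval and temperature are not named in the data-collection section and may have to be extracted from operative records. The interval will also overlap with bypass time, so it may add little precision.

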Type I error. The significance level will be 0.025 for the 1-tailed noninferiority tests for the primary outcome and for each set of the secondary outcomes, and 0.05 for each of the 2-tailed superiority tests for tertiary outcomes (i.e., no adjustment for multiple testing for tertiary outcomes).

Our primary hypothesis is that HES 130/0.4 is noninferior to standard care effects on **mean urinary NGAL** measured within one hour of arrival to ICU and 24 following completion of surgery. We a priori define the noninferiority delta for urinary NGAL as a ratio of geometric means (since NGAL data are expected to be lognormal) of 1.15, for an effective delta of 15% of the control group mean. [Note: for this and other outcomes, if the data are non-normal, a log-transformation will be attempted and the treatment effect (if normal on the log-scale) will be summarized as the ratio of geometric means, equivalent to the difference in means of the log-transformed data.] As noted below under “Continuous outcomes measured over time (Primary and Secondary Aims)”, we will assess the treatment effect for the primary outcome in the context of a linear mixed model which allows us to simultaneously assess the effect across the collapsed time points if there is no group-time interaction, or else at specific times if there is an interaction detected. We will conduct tests for noninferiority using treatment effect estimates from the linear mixed model and applying 1-tailed t-tests for noninferiority as described in Mascha and Sessler (2011) [Mascha EJ, Sessler DI: Statistical grand rounds: Equivalence and noninferiority testing for regression models and repeated measures designs. Anesth Analg 2011; 112: 678–87], and with t-statistic as follows:

$$T_{NI} = \frac{\hat{\beta}_1 + \delta}{SE_{\hat{\beta}_1}}, \text{ where } \hat{\beta}_1 \text{ is the estimated treatment effect with standard error}$$

$SE_{\hat{\beta}_1}$ and noninferiority delta of δ .

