Interim monitoring analyses. We will conduct interim analyses for the parameter urinary NGAL (assessing safety [i.e., noninferiority] and non-safety [i.e., noninferiority not found]) at every 1/6th (16.7%) of the maximum enrollment of 130 patients, or approximately at every 22 or 23 patients, in a group sequential design. We will use the gamma spending function with gamma of -5 for safety (alpha spending; very conservative, like O-Brien-Fleming boundaries) and gamma of 0 for futility, or non-safety (beta spending; fairly aggressive, like Pocock boundaries). We spend the beta faster than the alpha in order to be able to detect any potential harm of the treatment as early as possible in the trial. Table 3 gives the P-value boundaries for efficacy and futility at each interim look (columns 5 and 6). Column 2 gives the total sample size at each look. The last 2 columns give the probability of crossing a boundary when the null hypothesis is true (Under H0) and when the alternative (noninferiority) is true (H1). For example, if Voluven is truly noninferior, the probability of crossing the safety boundary is 3.1% at the first look, $3.1\% + 12.7\% = 16\%$ through the second look, and so on. The below figure displays the boundaries on the z-scale (A) and the error spending functions (B) for this design.

Table 3. Interim Monitoring -- Group Sequential Design Boundaries							
Information action	Cumulative Accrual	Alpha Spent	Beta Spent	P-value Boundaries		Boundary Crossing Probabilities	
				Safety H0	Non-safety H1	Under H0 For nonsafety	Under H1 For safety
0.167	22	0.0004	0.017	<0.001	0.746	0.254	0.031
0.333	43	0.001	0.033	0.001	0.471	0.303	0.127
0.500	65	0.003	0.050	0.002	0.256	0.217	0.229
0.667	86	0.006	0.067	0.005	0.125	0.122	0.252
0.833	108	0.013	0.083	0.010	0.056	0.060	0.183
1.000	130	0.025	0.100	0.021	0.021	0.025	0.078

A. Z-statistic Stopping boundaries

B. Alpha and beta spending functions

Sample size calculations (Aim 1):

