Sample size is based on assessing the noninferiority of HES 130/0.4 to 5% albumin on the primary outcome of urinary NGAL. In patients undergoing cardiac surgery, Koyner et al (2012)²⁹ observed median [quartile] urinary NGAL values of 28.3 (13.5–82.9) in patients who did not progress to renal failure and 72.1 (11.4–495.6) in patients who progressed to renal failure. Assuming that NGAL values follow a log-normal distribution as in previous studies, we can use the above observed quartiles to estimate the mean, standard deviation and coefficient of variation (CV) for the above groups, yielding CV of 2.3% and 50%, respectively. Assuming for the current study a coefficient of variation between these values, or 25%, we would need 52 patients per group (total of 104) to have 90% power at the 0.025 significance level to be able to claim noninferiority of HES to albumin using a noninferiority delta of a ratio of geometric means of 1.15. These calculations assume no treatment-time interaction and therefore no Bonferroni correction for comparing groups at each of two time points within an outcome. Based on the above calculations, a sample size of 110 would suffice for a study with no interim monitoring. **Adjusting for the interim monitoring at each one-sixth of the total, a maximum sample size of 130 patients are required. Allowing for 5 potential dropouts and 5 pilot patients (which will not be included in the analyses), we will plan for a potential total of 140 patients.**

STUDY PROCEDURES

Quality Assurance

The major components of quality assurance will be staff training, the standardization of data collection, entry, and processing, and ongoing monitoring to ensure timeliness and accuracy of study data. All study protocols and forms will be compiled into two operations manuals (one for the clinical sites and one for data management) that will be revised as necessary. A clinical reference manual will be created and will include administration and scoring criteria, specific testing instructions and inclusion and exclusion criteria for diagnosis and study ascertainment. This manual will also contain copies of test forms and will be available to all study personnel from a password-protected web site. The current manual for data management will be made easily available to data management personnel and used for continued training. This manual will include a question-by-question written script for interviewing purposes.

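### Table 3's safety boundaries correspond to gamma = -4, not the gamma = -5 stated in the text

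*Combined protocol and SAP*

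**What the plan says.** Under Statistical Methods, Interim monitoring analyses, urinary NGAL is to be tested in a group sequential design with looks "at every 1/6th (16.7%) of the maximum enrollment of 130 patients". For the safety (noninferiority) boundary the plan states: "We will use the gamma spending function with gamma of -5 for safety (alpha spending; very conservative, like O-Brien-Fleming boundaries". For the non-safety boundary it states "gamma of 0 for futility, or non-safety (beta spending; fairly aggressive, like Pocock boundaries".

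The thresholds themselves are left to the table: "Table 3 gives the P-value boundaries for efficacy and futility at each interim look (columns 5 and 6". As an example of reading the table, the text says that if HES is truly noninferior, "the probability of crossing the safety boundary is 3.1% at the first look".

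The overall error rates are given elsewhere. The Type I error paragraph says "The significance level will be 0.025 for the 1-tailed noninferiority tests for the primary outcome", and the sample size section gives "90% power at the 0.025 significance level". The Executive Committee section adds that the interim analyses are to be programmed ahead of time.

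**The concern.** A spending function, its total alpha and the look times fix the boundaries completely. The text and the table should therefore be two descriptions of one design, and the alpha-spent column does not fit the stated gamma. At the first look the table spends 0.0004, where gamma = -5 spends 0.0002.

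The safety boundary decides when enrolment may stop with a claim that HES is noninferior on NGAL, the only outcome the plan treats as confirmatory. A programmer who enters the stated gamma gets thresholds that the table contradicts. A P value that falls between the two sets would stop the trial under one and not the other. If this surfaces only after an interim P value has been seen, any choice between them could look data-driven.

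**Working it through.** **Inputs.** One-sided alpha 0.025 (Type I error). Power 90%, so total beta 0.10 (Sample size calculations). Six looks at information t = 1/6, 2/6, …, 1, alpha spending with gamma = -5 and beta spending with gamma = 0 (Interim monitoring analyses).

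**Step 1: alpha spent.** For the gamma family,

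alpha(t) = 0.025 × (1 − exp(−gamma·t)) / (1 − exp(−gamma)).

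At the first look, t = 1/6:

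- gamma = -5: 0.025 × (1 − 2.301) / (1 − 148.41) = 0.025 × 0.00883 = 0.00022
- gamma = -4: 0.025 × (1 − 1.948) / (1 − 54.60) = 0.025 × 0.0177 = 0.00044

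| Look | Table 3 | gamma = -4 | gamma = -5 |
|---|---|---|---|
| 1 | 0.0004 | 0.00044 | 0.00022 |
| 2 | 0.001 | 0.00130 | 0.00073 |
| 3 | 0.003 | 0.00298 | 0.00190 |
| 4 | 0.006 | 0.00625 | 0.00458 |
| 5 | 0.013 | 0.01261 | 0.01077 |
| 6 | 0.025 | 0.025 | 0.025 |

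At the printed precision gamma = -5 fails at looks 1, 3, 4 and 5; gamma = -4 fits all six. Values of gamma from about -4.05 to -3.98 are the only ones that fit all five interim entries. Two alternative explanations were tried. Replacing k/6 by accrual fractions (22/130, 43/130 and so on) gives 0.00023, 0.00072, 0.00190, 0.00446 and 0.01063 with gamma = -5, which still misses. A Lan-DeMets O'Brien-Fleming function gives less than 0.00001, then 0.0001, 0.00153, 0.00605 and 0.01408, which does not match either.

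**Step 2: boundaries and crossing probabilities.** These come from recursive numerical integration, with beta(t) = 0.10·t, a non-binding non-safety boundary and the drift solved for 90% power. With gamma = -4 the remaining columns of Table 3 are reproduced to the printed precision:

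- Non-safety P: 0.746, 0.471, 0.256, 0.125, 0.056, 0.021
- Non-safety crossing under H0: 0.254, 0.303, 0.217, 0.122, 0.060, 0.025
- Safety P and safety crossing under H1: as below

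| Look | Safety P, Table 3 | gamma = -4 | gamma = -5 | H1 crossing, Table 3 | gamma = -4 | gamma = -5 |
|---|---|---|---|---|---|---|
| 1 | <0.001 | 0.00044 | 0.00022 | 0.031 | 0.031 | 0.020 |
| 2 | 0.001 | 0.00096 | 0.00055 | 0.127 | 0.127 | 0.101 |
| 3 | 0.002 | 0.00212 | 0.00142 | 0.229 | 0.229 | 0.215 |
| 4 | 0.005 | 0.00461 | 0.00360 | 0.252 | 0.252 | 0.266 |
| 5 | 0.010 | 0.0099 | 0.0090 | 0.183 | 0.183 | 0.208 |
| 6 | 0.021 | 0.0209 | 0.0222 | 0.078 | 0.078 | 0.090 |

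The H1 crossing column misses gamma = -5 at every look. The worked example of 3.1% is a gamma = -4 result; gamma = -5 gives 2.0%.

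**Step 3: consequences.**

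- Probability of a safety stop by look 3 if HES is noninferior: 0.031 + 0.127 + 0.229 = 38.7% under the table; 0.0200 + 0.1006 + 0.2148 = 33.5% under gamma = -5.
- Alpha spent, table's design relative to stated design: 0.00044/0.00022 = 2.0 at look 1; 0.00130/0.00073 = 1.8 at look 2.
- Sample size inflation for sequential monitoring: 1.225 (gamma = -4) and 1.218 (gamma = -5).
- Total alpha if the gamma = -4 boundaries are used at looks 1 to 5 and the gamma = -5 boundary at the end, ignoring the non-safety boundary: 0.0261. If the non-safety boundary is always obeyed, the same mixture gives 0.0207.

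**The case against.** The text prints no thresholds of its own. It delegates them to Table 3, and its worked example agrees with the table, so this may be one mistyped parameter in one sentence. That is plausible, but it shows only that the table is internally coherent. The documents do not say which gamma was intended or which source governs, and N = 130 cannot settle it because the two inflation factors are so close.

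The second objection is that little depends on it. Used consistently, either version spends exactly 0.025. If the non-safety boundary is followed, the actual type I error is about 0.020 under both. The safety thresholds differ by 0.0002 to 0.0013 in P, and at looks 1 and 2 they round to the same printed entries. The non-safety boundaries, which are there to catch harm early, barely move (0.746 against 0.748 at look 1). The doubling of alpha at look 1 is 0.0002 in absolute terms. All of this stands and limits the weight of the point. In particular, 0.0261 is not what the plan implies. It needs someone to mix the two versions and to treat the non-safety boundary as advisory, and Table 3 prints its own final boundary.

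None of this removes the contradiction. The gap exceeds rounding, and a final P of 0.0215 would meet the gamma = -5 threshold and fail the gamma = -4 threshold behind the table.

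**Conclusion.** The concern holds. The stated alpha-spending parameter and Table 3 describe different designs: the table, including the worked example, is the gamma = -4 design to the printed precision. That gamma = -4 was entered is an inference from this match; the documents do not say so.

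The size is modest. The table's design is the less conservative at each interim look and slightly stricter at the final one, and it raises the chance of an early safety claim by look 3 by about 5 percentage points when HES is noninferior. Type I error is at risk only if the versions are mixed and the non-safety boundary is overridden, and then by 0.0011 (0.0261 − 0.025). Maximum sample size, power and harm monitoring are essentially unaffected.

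The calculation assumes six equally spaced looks, one-sided alpha 0.025, total beta 0.10 spent linearly, and a non-binding non-safety boundary. The boundary figure is not shown in the available text and was not checked. The point should be corrected because it concerns the decision rule for the trial's one confirmatory conclusion.

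**What to change.** Make the text and table agree on one gamma before any interim P value is seen. There are two ways:

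1. Change the stated gamma to -4 and keep Table 3 and the worked example. This costs one number in the text.
2. Keep gamma = -5 and replace Table 3 (alpha spent, both P-value columns, crossing probabilities) and the worked example. This costs one rerun of the boundary program. By the calculation above, the safety P values would be 0.00022, 0.00055, 0.00142, 0.0036, 0.0090 and 0.0222.

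In either case, check that the boundary figure matches, print the P-value boundaries to at least four decimals, since an entry of <0.001 cannot be applied as a threshold, and state whether the non-safety boundary is binding. If any look has already taken place, record which boundaries were applied. Neither route changes enrolment, follow-up or data collection.
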